1.6. New Lesions

The appearance of new malignant lesions denotes disease progression; therefore, some comments on detection of new lesions are important. There are no specific criteria for the identification of new radiographic lesions; however, the finding of a new lesion should be unequivocal: i.e. not attributable to differences in scanning technique, change in imaging modality or findings thought to represent something other than tumor (for example, some ‘new’ bone lesions may be simply healing or flare of pre-existing lesions). This is particularly important when the patient’s baseline lesions show partial or complete response. For example, necrosis of a liver lesion may be reported on a CT scan report as a ‘new’ cystic lesion, which it is not.

A lesion identified on a follow-up study in an anatomical location that was not scanned at baseline is considered a new lesion and will indicate disease progression. An example of this is the patient

who has visceral disease at baseline and while on study has a CT or MRI brain ordered which reveals metastases. The patient's brain metastases are considered to be evidence of progressive disease even if he/she did not have brain imaging at baseline. If a new lesion is equivocal, for example because of its small size, continued therapy and follow-up evaluation will clarify if it represents truly new disease. If repeat scans confirm there is definitely a new lesion, then progression should be declared using the date of the initial scan.

1.7. Evaluation of Best Overall Response

The best overall response is the best response recorded from the start of the treatment until the end of treatment taking into account any requirement for confirmation. The patient's best response assignment will depend on the findings of both target and non-target disease and will also take into consideration the appearance of new lesions.

Revised Response Evaluation Criteria in Solid Tumors (RECIST) Version 1.1 ([Eisenhauer, 2009](#)) is summarized in the table below.

Response According to Revised Response Evaluation Criteria in Solid Tumors (Version 1.1) in Patients with Target (and Non-Target) Lesions When Confirmation is Required

Target Lesions	Non-target Lesions	New Lesions	Overall Response	Best Overall Response when Confirmation is Required
CR	CR	No	CR	≥ 4 weeks confirmation
CR	Non-CR/non-PD*	No	PR	
CR	Not evaluated	No	PR	
PR	Non-CR/non-PD/not all evaluated	No	PR	
SD	Non-CR/non-PD/not all evaluated	No	SD	Documented at least once ≥ 4 weeks from baseline
Not all evaluated	Non-PD	No	NE	
PD	Any	Yes or no	PD	No prior SD, PR, or CR
Any	PD**	Yes or no	PD**	
Any	Any	Yes	PD	

Abbreviations: CR=complete response; PD=progressive disease; PR=partial response; SD=stable disease; NE=not evaluable.

*For non-target disease, 'non-CR/non-PD' is preferred over 'SD' since SD is increasingly used as endpoint for assessment of efficacy in some trials, so to assign this category when no lesions can be measured is not advised.

**In exceptional circumstances, unequivocal progression in non-target lesions may be accepted as PD.

Note: Patients with a global deterioration of health status requiring discontinuation of treatment without objective evidence of disease progression at that time should be reported as "symptomatic deterioration." Every effort should be made to document the objective progression even after discontinuation of treatment.

Best Overall Response When Confirmation of CR and PR are Required

Overall Response, First Time Point	Overall Response, Subsequent Time Point	Best Overall Response
CR	CR	CR
CR	PR	SD, PD, or PR*
CR	SD	SD if minimum criteria for SD duration met, otherwise PD
CR	PD	SD if minimum criteria for SD duration met, otherwise PD
CR	NE	SD if minimum criteria for SD duration met, otherwise NE
PR	CR	PR
PR	PR	PR
PR	SD	SD
PR	PD	SD if minimum criteria for SD duration met, otherwise PD
PR	NE	SD if minimum criteria for SD duration met, otherwise NE
NE	NE	NE

Adapted from ([Eisenhauer, 2009](#))

NCI-CTCAE	National Cancer Institute-Common Terminology Criteria for Adverse Events
ORR	Objective response rate
OS	Overall survival
PD-1	Programmed death-1 (receptor)

PD-L1	Programmed death ligand 1
PD-L2	Programmed death ligand 2
PFS	Progression-free survival
PK	Pharmacokinetic
PR	Partial response
PT	Preferred term
Q3W	Every 3 weeks
RECIST	Response Evaluation Criteria in Solid Tumors
Regeneron	Regeneron Pharmaceuticals, Inc.
SAE	Serious adverse event
SAF	Safety analysis set
SAP	Statistical analysis plan
SAS	Statistical Analysis System
SC	Subcutaneous
SD	Stable disease
SOC	System organ class
TEAE	Treatment-emergent adverse event
TSH	Thyroid-stimulating hormone
WBC	White blood cell
WHO	World Health Organization

1. OVERVIEW

The purpose of the statistical analysis plan (SAP) is to ensure the credibility of the study results by pre-specifying the statistical approaches for the analysis of study data prior to database lock. The SAP is intended to be a comprehensive and detailed description of the strategy and statistical methods to be used in the analysis of data for R2810-ONC-ISA-1981 study.

This plan may be revised during the study to accommodate protocol amendments and/or to make changes to adapt to unexpected issues in study execution and/or data that affect planned analyses. The final plan, if revised, will document all changes and be issued prior to database lock.

1.1. Background/Rationale

1.1.1. Background

The global annual incidence of cervical cancer is approximately 527,000 cases per year, and there are approximately 265,000 deaths ([Torre, 2015](#)). Most cases are due to infection with human papillomavirus (HPV). Although vaccination against high risk strains of HPV is projected to gradually decrease the global incidence of cervical cancer in the next 15 years, the burden of this disease remains profound ([Bray, 2012](#)). Internationally, the etiologic fraction of HPV-associated malignancy, based on HPV detection, varies by geography and anatomic site, but overall suggests that 70% of cervical cancers are caused by HPV16/18, and HPV16 is the primary oncogenic virus in other anogenital and oropharyngeal cancers.

Cemiplimab is a high-affinity, recombinant human immunoglobulin G (IgG4P) monoclonal antibody that binds to programmed cell death 1 (PD-1) and blocks its interaction with programmed death ligand 1 (PD-L1) and programmed death-ligand 2 (PD-L2), countering PD-1-mediated inhibition of the anti-tumor immune response. Cemiplimab is being evaluated in more than 20 phase 1 through phase 3 clinical studies in a variety of tumor types. The safety profile of cemiplimab demonstrated in these clinical trials is consistent with the expected safety profile of an anti-PD-1 antibody. LIBTAYO® (cemiplimab) is approved for the treatment of patients with metastatic cutaneous squamous cell carcinoma or patients with locally advanced cutaneous squamous cell carcinoma who are not candidates for curative surgery or curative radiation.

ISA101b is a therapeutic vaccine targeting the HPV type 16 E6/E7 proteins. The HPV16 synthetic long peptides in ISA101b act as a therapeutic vaccine that stimulates the actions of both CD4+ T-helper cells and CD8+ cytotoxic T-cells against the known oncogenic sequences of the HPV16 virus.

1.1.2. Rationale

Combination therapy may stimulate convergent aspects of host immunity by employing complementary immunomodulators and immune-stimulatory aspects of conventional modalities. Combination therapy may result in the development of more effective cancer therapies.

Treatment with the PD-1 inhibitor pembrolizumab has shown initial efficacy as monotherapy in recurrent or metastatic cervical cancer after disease progression on or after chemotherapy ([FDA, 2018](#)). While the response rates with monotherapy Pembrolizumab are similar to chemotherapy in the 2L or greater setting, responses with pembrolizumab have shown greater durability

([Takeuchi, 1991](#); [Look, 1998](#); [Bookman, 2000](#); [Muggia, 2004](#); [Muggia, 2005](#); [Schilder, 2005](#); [Miller, 2008](#); [Lorusso, 2010](#); [Chung, 2019](#)).

ISA101 has demonstrated a robust and clinically active immune responses against HPV16 E6/E7 in HPV16 positive patients with pre-malignant lesions, such as vulvar intraepithelial neoplasia (VIN) ([Kenter, 2009](#); [van Poelgeest, 2016](#)). A single arm study in women with HPV16+ advanced cervical cancer receiving ISA101/101b after carboplatin and paclitaxel showed a potent and durable immune response to HPV16 epitopes. An increase in OS was associated with strength of induced vaccine responses ([Meliaf, 2020](#)). Data from a combination study with ISA101b and nivolumab in a variety of recurrent/metastatic incurable HPV16 positive malignancies showed an ORR of 33% with a safety profile consistent with PD-1 inhibitors ([Gillison, 2016](#)).

These data together support a single arm phase 2 trial with combination therapy of ISA101b and cemiplimab in recurrent/metastatic cervical cancer.

1.2. Study Objectives

1.2.1. Primary Objectives

The primary objective of the study is to estimate the clinical benefit of cemiplimab + ISA101b after progression on first line chemotherapy, as assessed by objective response rate (ORR).

1.2.2. Secondary Objectives

The secondary objectives of the study are:

- To characterize the safety profile of cemiplimab + ISA101b
- To assess preliminary efficacy of cemiplimab + ISA101b as measured by duration of response (DOR), progression-free survival (PFS), and overall survival (OS)

1.2.3. Exploratory Objectives

The exploratory objectives of the study are:

- To correlate clinical efficacy with baseline tumor tissue immune biomarkers including PD-L1, immune cell subsets, MHC class I/II, gene expression profile and tumor mutational burden.
- To correlate clinical efficacy with on-treatment changes in HPV antigen specific T cell responses, immune cell subsets and serum cytokine biomarkers
- Explore novel molecular and cellular predictive and pharmacodynamic biomarkers associated with clinical efficacy, including cellular and molecular parameters in tumor tissue and peripheral blood.
- To assess the immunogenicity of cemiplimab when combined with ISA101b
- To explore other HPV serotypes present in HPV16+ tumors

1.2.4. Modifications from the Statistical Section in the Final Protocol

TTR, DCR, and dDCR were added as secondary endpoints.

1.2.5. Revision History for SAP Amendments

This is the second version of the SAP, based on the study protocol of R2810-ONC-ISA-1981 Amendment 2 dated August 31, 2021.

The main changes from SAP 1.0 dated November 3, 2020 (based on the original protocol) include:

- Updated the sample size to 105 patients per protocol amendment 2
- Removed statistical hypothesis testing and added the option for an administrative efficacy review per protocol amendment 2
- Removed safety analysis set per protocol amendment 2. The full analysis set will be used to summarize efficacy, safety, and baseline variables.

2. INVESTIGATION PLAN

2.1. Study Design

This is a single-arm, phase 2, global study of treatment with cemiplimab + ISA101b in HPV16 positive cervical cancer patients with disease progression on first line chemotherapy in the recurrent or metastatic setting.

2.2. Sample Size and Power Considerations

The planned total sample size for this study is 105 patients.

The primary objective of the study is to estimate the clinical benefit of cemiplimab + ISA101b after progression on first line chemotherapy, as assessed by objective response rate (ORR).

With 105 patients, [Table 1](#) below presents various response rates and associated 2-sided 95% CIs using a normal approximation of the binomial distribution, and precision of estimation defined as distance from the boundary to the center (i.e., half-width of the 95% CI). If observed ORR ranges from 20.0% to 34.3%, the precision estimation using 105 patients ranges from 7.7% to 9.1%.

Table 1: The 2-sided 95% Confidence Intervals for Observed ORR Based on a Sample Size of 105 Patients

Number of Responders	Observed ORR	95% CI	Precision
21	20.0%	(12.4, 27.7)	7.7%
24	22.9%	(14.8, 30.9)	8.0%
27	25.7%	(17.4, 34.1)	8.4%
31	29.5%	(20.8, 38.3)	8.8%
36	34.3%	(25.2, 43.4)	9.1%

2.3. Study Plan

After a screening period of up to 28 days, all patients will receive the following regimen:

- ISA101b 100 µg/peptide by SC injection on Day 1, Day 29, and Day 50 (total of 3 doses).
- Cemiplimab 350 mg given by IV infusion over 30 minutes every 3 weeks (Q3W) on Days 8 and 29 in Cycle 1, on Days 1 and 22 in Cycles 2 through 4, and on Days 1, 22, and 43 in all subsequent cycles or until disease progression or discontinuation of study drug for any other reason.

Cycle 1 will be 7 weeks long, Cycles 2 through 4 will be 6 weeks long, and all subsequent cycles will be 9 weeks long.

Patients will be assessed for response at week 7, then every 6 weeks for 3 cycles, then every 9 weeks in all subsequent cycles or until disease progression or discontinuation of study drug for any other reason. Patients with confirmed CR after a minimum of 48 weeks of treatment may elect

to discontinue treatment and continue with all relevant study assessments (eg, efficacy assessments).

There will be a 90-day safety follow-up after the last dose of cemiplimab. Patients who discontinue study drug for reasons other than progression will be followed approximately every 4 months by scans until disease progression or until the patient commences another anticancer systemic therapy, whichever comes first. After progression, survival follow-up should occur approximately every 4 months.

3. ANALYSIS POPULATIONS

In accordance with guidance from the International Conference of Harmonization of Technical Requirements for Registration of Pharmaceuticals for Human Use (ICH) guideline ICH E9 Statistical Principles for Clinical Trials ([ICH, 1998](#)), the following population of analysis will be used for all statistical analysis:

3.1. Full Analysis Set (FAS)

The full analysis set (FAS) includes all enrolled patients who received any study drug. Efficacy, safety, and baseline variables will be analyzed or summarized using the FAS.

3.2. The Pharmacokinetic Analysis Set

The PK analysis population includes all patients who received any study drug and who had at least 1 non-missing result following the first dose of cemiplimab.

3.3. Immunogenicity Analysis Set

The ADA analysis set includes all patients who received cemiplimab and had at least 1 non-missing ADA result following the first cemiplimab dose.

4. ANALYSIS VARIABLES

4.1. Demographic and Baseline Characteristics

The following demographic and baseline characteristics variables will be summarized:

- Age at screening in years (quantitative and qualitative variable: <65, ≥ 65 - < 75, ≥ 75)
- Race (American Indian/Alaskan Native, Asian, Black/African American, Native Hawaiian/Other Pacific Islander, White, and Other)
- Ethnicity (Hispanic/Latino or not)
- Weight (kg)
- Height (cm)
- Body mass index (BMI) calculated from weight and height: weight (kg) / [height (m)]²
- ECOG performance status (0, 1)

Baseline tumor characteristics variables include:

- Primary diagnosis
- Time from initial diagnosis to first study dose
- Histologic grade
- Cancer stages at initial diagnosis

4.2. Medical History

Medical history will be coded to a Preferred Term (PT) and associated primary System Organ Class (SOC) according to the latest available version of Medical Dictionary for Regulatory Activities (MedDRA®).

4.3. Pre-Treatment / Concomitant Medication

Medications/Procedures will be recorded from the day of informed consent until 90 days after the last study treatment or 1 day prior to starting a new treatment for cervical cancer, whichever is first. Medications will be coded to the ATC level 2 (therapeutic main group) and ATC level 4 (chemical/therapeutic subgroup), according to the latest available version of WHO Drug Dictionary (WHODD). Patients will be counted once in all ATC categories linked to the medication.

Prior cancer related medications/procedures: medications taken, or procedures performed prior to administration of the study drug, particularly, prior cancer related surgery, prior cancer related radiotherapy, and prior cancer related systemic therapy will be summarized.

Pre-treatment medications/procedures: non-study medications for which administration started and discontinued before a patient received the first dose of study drug.

Concomitant medications/procedures: any treatment administered from the time of informed consent until 90 days after the last study treatment or start of another systemic anticancer therapy, whichever comes first, will be considered concomitant treatment. This includes medications and other therapies for which administration started 30 days before the first dose of the study and will continue during the study, as well as any therapies started in the follow-up period to treat a study-drug-related AE.

Post treatment anti-cancer medications/procedures: anti-cancer medications and other anti-cancer therapies that started after discontinuation of the study drug.

4.4. Efficacy Variable

4.4.1. Primary Efficacy Variable

Overall response is determined by RECIST version 1.1 ([Eisenhauer, 2009](#)).

Best overall response (BOR) is determined once all the overall response data for the patient are known. The best overall response is the best response recorded during the study:

- Best overall response of CR or PR must be confirmed by consecutive evaluations of overall response of CR or PR at time points at least 4 weeks apart.
- Best overall response of SD must have met the response SD criteria at least once \geq 42 days (7 weeks - 7 days) after start of study treatment. Best overall response of (early) PD does not require confirmation using the RECIST.
- The best overall response for patients who do not have any post-baseline tumor assessment will be not evaluable (NE). Patients with best overall response of NE will be considered as not reaching an objective response of CR or PR.

Objective response rate (ORR) is determined by the proportion of patients with best overall response of CR or PR in the FAS.

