The total duration of study from start of screening to final analysis of OS is expected to be approximately 36 months (approximately 12 months of accrual, approximately 12 months of treatment, and approximately 12 months of follow up).

Figure 2: Study Flow Diagram

¹ Withdrawal due to reasons as listed in Section 7.3 and Section 8.2.2.

End of treatment is defined as the end of study drug. Patients may discontinue study drug for progression of disease or for any reason listed in Section 7.3 and Section 8.2.2. Thirty days after the last dose of study drug, patients will have EOT visit. Ninety days after the last dose of study drug, patients will have the safety follow-up visit (Table 2).

A patient who progresses on treatment will have EOT visit and safety follow-up visit. End of study (EOS) disposition will be on or after the safety follow-up visit. They will then enter survival follow-up.

A patient who discontinues treatment for reasons other than progression, as listed in Section 7.3 and Section 8.2.2, will have EOT and safety follow-up visit. They will then have tumor assessments until progression or the start of another anticancer therapy. At progression or start of another anticancer therapy, patients will have EOS disposition and then enter survival follow-up.

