8.8. Treatment with Cemiplimab Beyond Disease Progression

It is recognized that a minority of patients treated with immunotherapy may derive clinical benefit despite initial evidence of progressive disease.

Patients who experience RECIST 1.1-defined progressive disease will be permitted to continue treatment until further progression is observed, provided the following criteria are met:

- Investigator assesses continued use of a PD-1 therapy is appropriate
- Patient continues to meet all other study eligibility criteria, as defined in the inclusion/exclusion criteria (Section [7.2](#))
- Patient is tolerant of cemiplimab and has a stable performance status.
- Patient provides written informed consent prior to resuming treatment by signing the current version of the ICF (eg, the patient repeats the written informed consent that was done prior to initial study enrollment).
- Patients do not have evidence of rapidly progressing disease

It is understood that, if there is further progression after resumption of treatment ($\geq 30\%$ increase in tumor burden from the time of initial progressive disease by RECIST criteria; this includes an increase in the sum of all target lesions and/or the development of new lesions), that cemiplimab will be discontinued.

Patients should continue with assessments according to [Table 2](#).

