11.4.3.1. Primary Efficacy Analysis

Primary efficacy analysis will be performed when the last patient enrolled has had the opportunity for at least 4 tumor assessments.

The primary endpoint for efficacy analyses is the investigator-assessed ORR as determined by RECIST version 1.1 ([Eisenhauer, 2009](#)). The ORR is defined as the proportion of patients who achieve a best overall response (BOR) of CR or PR. Patients who are not evaluable for BOR will

be considered as non-responders. The ORR along with the 2-sided 95% confidence interval using a normal approximation of the binomial distribution will be summarized.

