4.4.2. Secondary Efficacy Variables

Duration of response (DOR) is determined for patients with BOR of CR or PR. DOR is measured from the time measurement criteria are first met for CR/PR (whichever is first recorded) until the first date of recurrent or progressive disease (radiographic), or death due to any cause.

- Patients who do not have a documented tumor progression or death will be censored at the last evaluable tumor assessment.
- Patients who do not have a documented tumor progression or death before initiation of new anti-cancer therapy will be censored at the last evaluable tumor assessment prior to or on the date of new anti-cancer therapy.

Progression-free survival (PFS) is measured from the start of treatment until the first date of recurrent or progressive disease (radiographic), or death due to any cause.

- Patients who do not have a documented tumor progression or death will be censored at the last evaluable tumor assessment.

- Patients who do not have a documented tumor progression or death before initiation of new anti-cancer therapy will be censored at the last evaluable tumor assessment prior to or on the date of new anti-cancer therapy.
- Patients who do not have any evaluable post-baseline tumor assessment and do not die will be censored on the date of first study treatment.

Overall survival (OS) is measured from the start of treatment until death due to any cause. Patients who do not die will be censored at the last date that patient is documented to be alive. As many patients may receive new anti-cancer therapy after disease progression, a sensitivity analysis of OS will be conducted by censoring patients at the first date of a new anti-cancer therapy is taken.

Time to tumor response (TTR) is determined for patients with BOR of CR or PR. TTR is measured from the start of treatment until the time measurement criteria are first met for CR/PR (whichever is first recorded).

For all the above time-to-event variables, the time to event (day) is the date of event/censor - the date of first study treatment + 1.

Disease control rate (DCR) is determined by the portion of patients with BOR of CR, PR, or SD.

Durable disease control rate (dDCR) is defined as the proportion of patients best overall response of CR, PR, or SD without progression for at least 12 weeks.

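### SAP 4.4.1 does not stop best overall response at first RECIST 1.1 progression, so a confirmed response after progression can count in the primary ORR

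*SAP*

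**What the plan says.** - **SAP 4.4.1.** BOR is derived after all of a patient's response data are in. The window is given as: "The best overall response is the best response recorded during the study". CR and PR need consecutive CR/PR evaluations at least 4 weeks apart. PD as a BOR needs no confirmation, and the SAP puts the word early in parentheses before it. ORR is the share of the FAS with a BOR of CR or PR.
- **Protocol 11.4.3.1.** "The ORR is defined as the proportion of patients who achieve a best overall response (BOR) of CR or PR". It gives no time window.
- **Protocol Appendix 3, section 1.7.** BOR is the "best response recorded from the start of the treatment until the end of treatment", with allowance for any confirmation requirement. Protocol 6.1 adds: "End of treatment is defined as the end of study drug". In the first table of section 1.7, the entry for a BOR of PD carries the condition that no SD, PR or CR came before. The confirmation table has no row that starts with PD.
- **Protocol 8.8.** "Patients who experience RECIST 1.1-defined progressive disease will be permitted to continue treatment until further progression is observed". The conditions cover continued eligibility, tolerance, stable performance status, renewed consent and absence of rapid progression. Scans go on: "Patients should continue with assessments according to" Table 2.
- **SAP 4.4.2.** PFS and DOR both run "until the first date of recurrent or progressive disease (radiographic), or death due to any cause". DCR rests on the same BOR: "Disease control rate (DCR) is determined by the portion of patients with BOR of CR, PR, or SD".

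**The concern.** Protocol 8.8 expects some patients to benefit after initial progression and keeps them on study drug and on the scan schedule. The trial will therefore produce scans after PD. The SAP ends PFS and DOR at first PD but sets no matching limit for BOR. BOR decides who is a responder in the primary analysis, who counts in DCR, and who enters the DOR and TTR analyses.

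At stake is whether the endpoints agree with one another. The same patient could be a responder for ORR, a failure for PFS before the response began, and a case with no usable value for DOR. In an open-label, single-arm study whose only primary objective is to estimate an investigator-assessed ORR, the meaning of responder should not depend on how the SAP is programmed.

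**Working it through.** **1. The plan's own precision.** Half-width = 1.96 × √(p(1 − p)/105).
- 21 responders: p = 0.200, 1.96 × √(0.200 × 0.800/105) = 7.65 points.
- 36 responders: p = 0.343, 1.96 × √(0.343 × 0.657/105) = 9.08 points.

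Protocol Table 3 and SAP Table 1 print 7.7 and 9.1, so the stated range reproduces.

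**2. Nominal scan days.** Cycle 1 lasts 7 weeks and cycles 2 to 4 last 6 weeks each (protocol 6.1). Scans fall on day 50, then 50 + 42 = 92, 92 + 42 = 134 and 134 + 42 = 176.

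**3. Thresholds (Appendix 3, section 1.5.1).** PR is a fall of at least 30% from the baseline sum. PD is a rise of at least 20% and at least 5 mm from the smallest sum on study.

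**4. An SD–PD–PR patient.** Assumptions: no new lesions, non-target disease neither CR nor PD, and the conditions of protocol 8.8 met.

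| Scan | Sum (mm) | Change | Response |
|---|---|---|---|
| Baseline | 100 | – | – |
| Day 50 | 72 | −28% from baseline | SD |
| Day 92 | 87 | (87 − 72)/72 = +20.8%, +15 mm from nadir | PD |
| Day 134 | 70 | −30% from baseline | PR |
| Day 176 | 70 (assumed unchanged) | −30% from baseline | PR, 176 − 134 = 42 days later, so confirmed |

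**5. What each rule does with this patient.**
- SAP 4.4.1 read literally: BOR is PR, so the patient is a responder.
- Appendix 3 window read literally: also PR while study drug continues, because treatment beyond progression lies inside that window.
- PFS: event on day 92.
- DOR: from first response (day 134) to first PD (day 92) is 92 − 134 = −42 days.
- BOR stopped at first PD: SD, since the day-50 SD meets the SAP's 42-day minimum. The patient leaves ORR but stays in DCR.

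**6. How much reversal is needed.** PD is measured from nadir and PR from baseline, so a later PD is easier to reverse than a first-scan PD.
- Example above: (87 − 70)/87 = 19.5%. The limit, with a nadir just above 70 mm, is (84 − 70)/84 = 16.7%.
- First-scan PD at 120 mm: (120 − 70)/120 = 41.7%.

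**7. DCR.** A patient with SD before PD is in DCR either way, so only first-scan PD matters. Sums of 100, 121 and 119 mm give PD (+21%, +21 mm) and then SD (+19% from the nadir of 100), a fall of only 2/121 = 1.7%. On the literal SAP window this BOR is SD. The Appendix 3 entry points to PD.

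**8. Size.** One patient is 1/105 = 0.95 points. The documents give no count of patients who respond only after PD. Assuming 0 to 5 among 27 counted responders:

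| Post-PD responders removed | ORR | 95% CI |
|---|---|---|
| 0 | 25.7% | 17.4 to 34.1 |
| 1 | 24.8% | 16.5 to 33.0 |
| 2 | 23.8% | 15.7 to 32.0 |
| 3 | 22.9% | 14.8 to 30.9 |
| 5 | 21.0% | 13.2 to 28.7 |

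**The case against.** The best reply is that the documents already treat PD as final. The SAP describes PD as a BOR as early and asks for no confirmation. The Appendix 3 entry gives BOR of PD to a patient with no earlier SD, PR or CR, which fits every patient who progresses at the first scan and may explain why the confirmation table has no row starting with PD. DOR as defined presupposes that response comes before progression, so a reading that makes it negative is unlikely to be intended. Appendix 3 also refers to the RECIST 1.1 publication for full details, and that source is not available here.

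Much of this stands for first-scan PD, where BOR of PD is the natural reading. Even there, no sentence excludes a later confirmed response. For SD–PD–PR the hints run out: this patient has earlier SD, so the Appendix 3 condition for a BOR of PD is not met, and the progression is not early.

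It is also fair that the conditions in protocol 8.8 keep numbers down, and that the scan rules in protocol 6.1, 9.1.4 and 9.2.2.1 already stop follow-up imaging at new therapy. A new-therapy stop for BOR is therefore mainly for completeness.

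Two stronger readings are tempting and should not be drawn:
- **That the plan decides to count responses after progression.** No text says so. The supportable statement is that they can count and nothing excludes them.
- **That the differing Appendix 3 window changes the result**, for example by turning a PR seen at the last dose and confirmed off drug into SD. The Appendix 3 sentence allows for confirmation, and its table does not require the second scan to be on drug. The SAP-based ORR would not move in any case. Nor is that window a remedy, since it has no stop at PD either.

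**Conclusion.** The point holds as a gap in the primary endpoint definition. The literal SAP rule, combined with protocol 8.8, can make a responder of a patient whose PFS has already failed and whose DOR is negative or undefined. SD–PD–PR is the clear case. First-scan PD followed by response is less clear, because the wording leans towards PD as final.

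The size is 0.95 points of ORR per patient, against a planned half-width of 7.7 to 9.1 points. The number of patients is not given and is probably small, so no total shift is claimed. The worked example assumes target-lesion progression without new lesions. A response is harder to reach when PD came from a new lesion that persists.

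A reader might infer that ORR would be materially inflated. In the illustration, removing two of 27 responders takes the lower limit from 17.4% to 15.7%, across the 16.4% that protocol 1.2 cites for cemiplimab alone. The documents do not support that conclusion: the two patients are assumed, and protocol 11.1 sets no formal hypothesis or threshold. The case for change rests on a clear definition and agreement among endpoints. It should be settled before database lock.

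**What to change.** In SAP 4.4.1, replace the sentence that sets the BOR window with:

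> BOR uses assessments from first dose up to and including the first RECIST 1.1 PD, or the last evaluable assessment on or before the start of new systemic anticancer therapy, whichever is first. Post-treatment scans before that point count, including for confirmation. Responses after first PD are reported separately and are not in ORR or DCR.

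Give Appendix 3 section 1.7 the same window in place of the one that ends with treatment.

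The cost is a short SAP paragraph and one sentence in the protocol appendix. Sample size, visits and analysis timing do not change, and both documents provide for SAP revision before database lock. ORR may be slightly lower. DCR may be too, but only through patients whose first scan showed PD, since a patient with qualifying SD before PD stays in DCR. Benefit after progression remains visible in the separate report.
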